6.1.7 Withdrawal procedures

6.1.7.1 Withdrawal from trial

If a Subject withdraws consent from the trial after randomization (Visit 2), the Investigator must ensure every possible effort is made to undertake procedures same as those for end of treatment (Visit 14) including the meal test, as soon as possible after decision of ending trial. The meal test should be performed with trial product according to randomization unless this is not feasible due to safety reasons as judged by the Investigator.

The Subject should also complete the follow-up visit (Visit 15). Final drug accountability must be performed even if the Subject is not able to come to the trial site.

Although a Subject is not obliged to give his/her reason(s) for withdrawing from a trial, the Investigator must make a reasonable effort to ascertain the reason(s), while fully respecting the Subject's rights. Where the reasons are obtained, the primary reason for not completing the trial must be specified within the source documentation.

6.1.8 Crossover (Visit 8)

At Visit 8 cross over the subject's will be dispensed study medication and switched to the comparative trial product. The Subject's will be instructed to change their pumps to manual mode for 1 week after the start of the crossover period. After 7 days of manual mode then subject will turn on auto mode for the duration of the treatment period.

6.1.9 End of treatment (Visit 14)

At end of treatment (Visit 14), the trial product should be discontinued and a stop date of trial product must be recorded in the source documentation.

The Subject should be switched to a suitable marketed product at the discretion of the Investigator and this product should be recorded on the source documentation. For procedures to be performed at end of treatment (Visit 14), please see flowchart in section [2](#).

6.1.10 Follow-up

The follow-up period is a 30-day follow-up (Visit 15) relative to the end of treatment visit (Visit 14).

6.1.10.1 Follow-up (Visit 15)

During the 30-day follow-up period (Visit 15) the following information will be collected:

- AEs
- Concomitant medication
- Concomitant diabetes medication
- Hypoglycemic events
- Unexplained hyperglycemic events

6.2 Subject related information

6.2.1 Demography

The following demographic data will be obtained by the Investigator:

- Date of birth
- Age at screening
- Ethnicity

- Race
- Sex

6.2.2 Diagnosis of Type 1 Diabetes Mellitus

At screening (Visit 1) the date of diagnosis of T1DM, as part of the medical history intake, will be obtained.

6.2.3 Concomitant illness and medical history

A **concomitant illness** is any illness, except T1DM, that is present at the start of the trial (i.e. at screening (Visit 1) or found as a result of the screening procedures.

Any change to a concomitant illness should be recorded in the source documentation. A clinically significant worsening of a concomitant illness must be reported as an AE as described in section [12](#).

Medical history is a medical event that the Subject has experienced in the past. Only relevant medical history, as judged by the Investigator, should be reported.

The information collected for concomitant illness and medical history should include diagnosis, date of onset, date of resolution, or continuation, as applicable.

6.2.4 Childbearing potential

It must be recorded in the source documentation whether female Subjects are of childbearing potential.

Female of non-childbearing potential is defined as, but not limited to:

- A female who has undergone a hysterectomy, bilateral oophorectomy, uterine ablation or bilateral tubal ligation
- Postmenopausal defined as no menses for 12 months without an alternative medical cause
- Other medical reasons preventing childbearing potential

Pregnancy testing must be performed on females with childbearing potential, as described in Section [2](#).

The Subjects must be instructed to use approved contraceptive methods, throughout the trial and until 1 week after end of treatment.

6.3 Clinical assessments

6.3.1 Concomitant medication

A concomitant medication is any medication, other than trial products and diabetes medication which is taken during the trial, including in the screening, treatment, and follow-up periods.

Details of any concomitant medication must be recorded in the source documentation at screening (Visit 1). Any changes in concomitant medication must be recorded at each visit or phone contact as they occur. The information collected for each concomitant medication includes (at a minimum) trade name or generic name, indication, start date, and stop date (or continuation).

If a change is due to an AE, then this must be recorded and reported according to section [09](#).

6.3.2 Use of Pumps and BG meters

During the trial, from start of the randomization period (Visit 2) until end of treatment (Visit 14), each time the Subjects attends a site visit the following data will be uploaded to Medtronic CareLink (a web based database):

- All BG meter data transferred to the pump
- All pump data

Data uploaded from the insulin pump include SMPG values, insulin doses, dose calculation related data (e.g. carbohydrates, carbohydrate ratio and insulin sensitivity), primes and rewinds, alarms and other pump settings. Once data has been uploaded to Medtronic CareLink the Investigator will use the reports generated to:

- Check Subject treatment and compliance
- Make adjustments to the Subject's treatment
- Reconcile data entered in the Subjects diary

6.3.2.1 Insulin dose

It is recommended that the bolus dose should be established by Subjects using the Bolus Wizard[®] according to their usual practice based on instructions from the Investigator.

6.3.2.2 Self-measured plasma glucose

At Screening (Visit 1) the Subject will be required to use their personal BG Contour[®] meter and supplies during the study. If the subject is not able to use their own supplies, they will be provided with a BG Contour[®] meter, including lancets and test strips for BG meters. The Subject will be instructed verbally on how to use the device according to the

manufacturer's instructions, as needed. The Subject will also be provided with written instructions as needed. Sites will, as necessary, go through the instructions of use with the Subject during visits to the site.

Throughout the trial, only the BG Contour[®] meter specifically designed to pair with the Medtronic 670G pump must be used to measure the plasma glucose values.

The BG Contour[®] meter and the pump should be confirmed to be linked by the site personnel at Screening (Visit 1) by review and/or entering the BG Contour[®] meters Identifications number into the pump to ensure SMPGs are automatically transferred to the pump. The BG Contour[®] meter must be set to transfer all SMPG values automatically.

The Subjects must be instructed to bring their BG Contour[®] meter to the site at every visit. The site personnel must upload the data from the BG Contour[®] meter into Medtronic CareLink at every site visit.

The Investigator will be able to review the SMPG profiles in Medtronic CareLink reports and use them to evaluate the Subject's glycemic control and make adjustments to the pump settings in order to optimize insulin titration.

For the following episodes additional information needs to be recorded in the diary:

- If a SMPG value is ≤ 70 mg/dL, the Subject should record the hypoglycemic episode.
- If a SMPG value is > 70 mg/dL, but the Subject feels typical symptoms of hypoglycemia and interprets those as indicative of hypoglycemia, the subject should record symptoms and glucose level.
- If an SMPG value is ≥ 300 mg/dL, the Subject should record only the unexplained hyperglycemic episodes.

The Investigator should check whether the Subject has recorded the episodes in the hypoglycemia and unexplained hyperglycemia section of the diary, by comparing the diary with the Medtronic CareLink report. If not, the missing information needs to be filled in by the Subject during the visit.

4-point self-measured plasma glucose profile

Subjects will be instructed to perform 4-point profiles every day during the conduct of the trial (from Visit 1 to Visit) mainly for titration purposes. The SMPGs should be measured at the following time points:

- Before breakfast

- Before lunch
- Before main evening meal
- At bedtime

SMPG measurements before breakfast should be performed in a fasting condition. SMPG measurements before lunch, main evening meal, and at bedtime should be performed before any bolus insulin infusion.

6.3.2.3 Change of infusion set and reservoir

Infusion sets will not be provided by the study. The subjects should be able to continue to afford and use their own personal infusion sets throughout the entire study period. The type of infusion set should be recorded in the source documentation at screening and the subjects should remain on the same type of sets throughout the duration of the entire study period.

The Subjects should be instructed to routinely change infusion set in intervals not exceeding 3 days (2 days for SureT[®] (Easy-set[®])). Infusion set and reservoir should be changed at the same time. The trial products should preferably be administered in the abdominal wall. The Investigator should ensure that the Subject is instructed in the following:

- The infusion region chosen should remain unchanged throughout the trial
- The infusion site should be rotated within the same region
- The infusion set should preferably be inserted in the same way

The Subject should change infusion set and reservoir at the site under supervision by the Investigator at randomization (Visit 2) and at end of treatment (Visit 14) due to the change from pre-trial insulin to trial product. The Investigator should evaluate the skin for any local skin irritation or skin infection at every office visit. Any abnormal clinically significant findings should be recorded as an infusion site reaction, as detailed in Section [7](#).

6.3.2.4 Training in pump use

At start of the screening period (Visit 1), the Investigator should ensure that the Subject knows how to use the insulin pump and perform appropriate training. The Investigator will repeat the training at the randomization visit. The Investigator should ensure that the Subjects know about the following:

- How to set the time and date on their pump
 - Importance of maintaining the correct time and date (e.g. when traveling or entering time changes due to daylight savings)
- How to ensure the SMPG values are recorded in the pump
- Pump settings including settings for basal rates and bolus doses

- Dose adjustment of insulin and use of Bolus Wizard[®]
- When to perform a routine and non-routine change of infusion set and reservoir
- How to report infusion set change information
- Filling reservoir from vials including priming of infusion set and checking for air in the infusion set before insertion of reservoir
- Carbohydrate counting
- Troubleshooting in case of hypoglycemia and hyperglycemia
- When and how to measure ketones
- Troubleshooting in case of pump failure or any technical problems with the pump
- Proper sensor change techniques and timing
- Auto mode features and use
- Use of acetaminophen in conjunction with sensor use
- Standard 3 hour active insulin time will be used. This may be changed at the investigators discretion
- Standard bolus speeds will be used
- Standard target of 120 mg/dL will be used during auto mode

The Subjects should be instructed to call the site in case of any episodes of pump failures (e.g. technical problems or software problems) as well as to contact the pump manufacturer's technical support. The Investigators should record this pump failure incident in the Subject medical record.

6.3.2.5 Training in diabetes and carbohydrate counting

All Subjects should have reinforced diabetes training including carbohydrate counting e.g. sessions with a diabetes educator, dietician or qualified site staff (i.e. diabetes specialized nurse) according to local practice.

It is the Investigators responsibility to ensure that the Subject is adequately trained during the trial and has a satisfactory knowledge in:

- Recognition of carbohydrates in commonly eaten foods
- Ability to count the carbohydrate content in typical portions of simple foods
- Ability to interpret a nutrition label for carbohydrate content
- Glycemic targets
- Preventing and treating hypoglycemia using carbohydrate foods
- Ability to sum up the carbohydrate content of a meal

6.3.3 Body measurements

Height (without shoes) will be measured at screening (Visit 1) only and recorded rounded to the nearest centimeter (cm).

Body weight should be measured in kilograms (kg) without overcoat and shoes, and wearing only light clothing. Body weight will be recorded to one decimal place.

The body weight should be assessed on the same calibrated weighing scale equipment throughout the trial, if possible.

BMI will be calculated by kg/m^2 .

6.3.4 Meal test

The Subject will undergo a standardized liquid meal test at certain visits (see section 2).

During that time 5 blood samples will be drawn, as specified in section 2. The samples will be analyzed by the local laboratory. The Subject must attend the meal test visits in a fasting condition. Bolus infusion and other medication which should be taken before, in a relation to or after a meal should be withheld until the meal test has been performed.

The Subject should before the meal test be instructed to:

- Follow normal routine regarding eating and exercise habits on the day prior to the meal test
- Refrain from intake of alcohol on the day prior to the meal test
- Change infusion set and reservoir prior to the visit so that the meal test is not completed on the day of a sensor change or on day 7 of the current sensor wear
- Take a correction bolus according to guidance from Bolus Wizard® if the PG value above the target level. There should be a minimum of four hours between any correction bolus dose and the start of the meal test.

Any hypoglycemic episodes from midnight before the meal test should be treated and the hypoglycemic episode should be recorded in the diary. At the investigator's discretion, the meal test should be re-scheduled within the visit window.

The Subject should have SMPG values within a range of 71-180 mg/dL before beginning the meal test and bolus insulin dosing. The SMPG values should be verified and recorded at the site before starting the meal test. If the Subject is not fasting or the SMPG value is outside the range, at the Investigators discretion, the meal test should be rescheduled within the visit window.. The Subject's body weight must be measured and a blood sample must be drawn two minutes before intake of the standardized liquid meal. The bolus insulin dose should be calculated by the Investigator based on the dose level of 0.1 unit/Kg body weight. The calculated dose should be

rounded to the nearest whole unit. The 0.1 unit/kg dose is chosen as an approximation of a clinically relevant bolus dose needed for the given size of a standardized meal for T1DM. The use of a weight-based insulin dose calculation for the meal test was specifically chosen to be used in the study in order to minimize inter-subject variability. Only a normal bolus type is allowed. The start of bolus infusion will be defined as time point 0. The Subject will have a carbohydrate-rich standardized meal served immediately after bolus infusion and must consume this as quickly as possible (within 15 minutes). The Investigator should confirm that the Subject consumed the required volume of the standardized liquid meal and actual clock time of start of infusion and meal consumption should be noted. The standardized meal will be provided by the site. The volume of the standardized meal to be consumed should be measured out by the Investigator to be the equivalent to 78 grams of carbohydrate.

Time points of blood glucose obtained during the meal test will be as follows: -2 min, 0 min, 30 min, 60 min, 120 min and 180 min.

No smoking or intake of meals and liquids will be allowed during the meal test, except for water.

If SMPG values ≤ 70 mg/dL are measured then the hypoglycemia should be treated according to site practice and the meal test should continue according to the Investigator's discretion. The hypoglycemic episode must be reported.

After the meal test, the Investigator should make sure that the Subject is safe to leave the site confirmed by an additional SMPG value.

6.3.5 Site insertion examination

The site insertion examination will be performed as outlined in the flow chart (section [2](#)). Site insertion examination will include a skin examination of the subjects preferred infusion set site insertion.

Any abnormal and/or clinically significant findings must be recorded in the Subject's medical record or reviewed for an adverse event.

Any clinically significant worsening from screening, as well as any new abnormal and clinically significant findings, must be reported as an AE in accordance with section 9.

6.3.6 Vital signs

Diastolic blood pressure, systolic blood pressure and pulse should be assessed while the Subject is in a sitting position after five minutes of rest. If the Subject is using antihypertensive medication to control the blood pressure, then the medication should be taken as usual prior to assessing vital signs.

Vital signs will be assessed according to the flow chart, please see section 2.

Any abnormal and/or clinically significant findings at screening (Visit 1) must be recorded in the Subject's medical record.

Any clinically significant deterioration of a pre-existing condition, as well as any new clinically significant signs or symptoms, should be reported as an AE in accordance with section [09](#).

6.4 Laboratory assessments

Except for urine pregnancy testing, all laboratory analyses will be performed by a local laboratory contracted by the Investigator. The local laboratory will provide all laboratory supplies for the sampling and transportation of all blood and urine samples taken during the trial.

Laboratory samples can be drawn on another day than on the day of the actual visit, as long as it is within the visit window, as stated in the flowchart in section [2](#).

If laboratory samples need to be retaken due to missing result(s) (e.g. hemolyzed, sample leaked during transit, sample not being conclusive, lost in transit, etc.), the Subject should be called in for resampling.

6.4.1 1,5-anhydroglucitol

1,5 –anhydroglucitol is measured in order to evaluate post prandial glucose control. Please see section [2](#).

6.4.2 HbA_{1c}

Blood samples will be drawn as specified in the flow chart (section [2](#)) to determine the HbA_{1c} level in order to evaluate glycemic control.

6.4.3 Pregnancy testing

For females of childbearing potential, a urine pregnancy test will be performed at the visits, as detailed in the flowchart in section [2](#). In addition, urine pregnancy tests will be performed locally during the trial if a menstrual period is missed or if deemed necessary by the Investigator or required by local law. A positive urine pregnancy test should be followed by a confirmatory serum-hCG (local laboratory).

6.4.4 Fructosamine

Fructosamine levels indicate the average level of blood glucose control over the past 2-3 weeks. Please see section [2](#).

6.5 Other assessments and procedures

6.5.1 Diary

Diaries will be used in this trial and handed out to the Subjects as specified in section [2](#). At End of treatment the Subjects have to return their last diaries.

The Investigator must carefully instruct the Subject in how to fill out the diary. The Subject should bring the diary at each visit to the site and there the Investigator or delegated site personnel must review the diary together with the Subject to ensure consistency/compliance. If clarification of entries is needed or discrepancies in the diary are found, the Subject must be questioned and a conclusion made in the Subject's medical record.

The following data will be captured by the Subject in the diary:

- Hypoglycemic episodes
- Unexplained hyperglycemic episodes (including any urine/blood ketone values measured, if available)

6.5.1.1 Hypoglycemic episodes

All plasma glucose values:

- ≤ 70 mg/dL
- > 70 mg/dL occurring in conjunction with hypoglycemic symptoms

Plasma glucose should always be measured and recorded by the Subject in the diary, when a hypoglycemic episode is suspected. Hypoglycemic episodes should be reported in the diary according to the instructions below throughout the trial from Visit 1 to End of treatment.

In case of several low SMPG values within the 60 minutes interval, the first value taken is the one that will be reported as the SMPG value for the hypoglycemic episode.

6.5.2 Occlusion event reporting

Starting from randomization (Visit 2) until the end of treatment (Visit 14) the subjects will be questioned at each visit on the occurrence of infusion set occlusions. Occlusion events, for this trial, are defined as a premature change of an infusion set prompted by suspicion of occlusion, leakage, or unexplained hyperglycemia. Subjects will be asked to return any infusion sets to the site, that are thought to have been occluded, for the site to view.

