To compare Fiasp[®] in terms of glycemic control with a focus on post-prandial 1-hour plasma glucose level and system-based outcomes to NovoLog[®] insulin when used in the Medtronic mini Med 670G HCL system (operating in auto-mode) in patients with type 1 diabetes.

Secondary objectives

- Assessment of post-prandial glucose regulation (Continuous glucose monitor data, and 1,5 anhydroglucitol levels)
- Evaluation of cumulative glycemic control (HbA1c)
- Measurement of HCL parameters
- Reporting of Fructosamine levels

Endpoints

Primary Endpoint

- Post-prandial 1-hour plasma glucose levels at 6 weeks into start of therapy in each arm

Secondary Endpoints

- Post- prandial 2- hour plasma glucose levels at 6 weeks into start of therapy in each arm
- HbA1c and 1, 5 AG levels prior to cross-over, and at end of study
- Glycemic excursion parameters: Time spent within glycemic ranges as below will be reported and analyzed. Time spent in specific ranges will be expressed as a percentage of total time on treatment.
 - o Time spent (%) within 70-180 mg/dl
 - o Time spent (%) < 70 mg/dl
 - o Time spent (%) >200 mg/dl
 - o Hypoglycemia (differentiated as level 1 or level 2) (Reference 11)
 - o Severe hypoglycemia
- Insulin related parameters

- Total daily dose
- change in %bolus and %basal from baseline
- Auto basal / basal amount (per day)
- Change in insulin : carbohydrate ratio from baseline
- Active insulin time
- Pump related parameters
 - Time spent (%) in auto mode
 - Time spent (%) in manual mode
 - Auto mode exits (with reasons for exit)
 - Infusion site reactions reported by patient
 - Occlusion events reported by patient

This is an exploratory, single-center, randomized, open label, active-controlled, complete cross-over trial comparing safety and efficacy of Fiasp[®] versus NovoLog[®] when used in the Medtronic MiniMed 670G system in subjects with T1DM.

Study timeline:

FPV expected to be April 2019 with LPV in January 2020. The total duration of the trial participation for subjects is approximately 20 weeks as shown below:

Visit 1: Screening

Visit 2: Randomization /Treatment Period 1 Start / Day 0

Visit 3: Phone visit / 1 day after randomization

Visit 4: Phone visit / 1 week after randomization

Visit 5: Office visit / Week 2

Visit 6: Phone visit / Week 4

Visit 7: Office visit / Week 6 / Meal test

Visit 8: Office visit / Week 7/ Treatment Period 2 Start

Visit 9: Phone follow-up / 1 day after Visit 8

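### The patient-reported occlusion endpoint rests on open-label suspicion and recall; report it split by reason, with a count of pump alarms from data already uploaded beside it

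*Combined protocol and SAP*

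**What the plan says.** Section 4 describes an "exploratory, single-center, randomized, open label, active-controlled, complete cross-over trial". Sections 4 and 12.4 both list, among the pump-related secondary endpoints, "Occlusion events reported by patient".

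Section 6.5.2 gives the definition: "Occlusion events, for this trial, are defined as a premature change of an infusion set prompted by suspicion of occlusion, leakage, or unexplained hyperglycemia". On collection, it says that "the subjects will be questioned at each visit on the occurrence of infusion set occlusions", from Visit 2 to Visit 14. It also asks subjects to bring back sets they believe were blocked so that the site can look at them. It gives no inspection criteria and no rule linking the inspection to the count.

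Section 6.5.1 introduces the diary content with "The following data will be captured by the Subject in the diary" and lists two items: hypoglycemic episodes and unexplained hyperglycemic episodes. Neither occlusions nor set changes are listed.

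Section 6.3.2 says that pump data sent to CareLink include "primes and rewinds, alarms and other pump settings". The stated uses are checking compliance, adjusting treatment and reconciling the diary. Section 10 adds CareLink reports to the material for general quality checks. Neither section assigns these data to the occlusion endpoint.

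**The concern.** Three features of the endpoint combine. The trigger is a suspicion held by someone who knows the product. The definition pools blockage with leakage and with unexplained high glucose, so a counted event need not be an occlusion. Collection depends on recall at contacts, with no dated entry made by the subject at the time.

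If subjects are more wary of one product, or report problems with it more readily, the count for that product rises with no difference in true occlusion. Section 12.1 says that all efficacy and safety endpoints will be summarized and analyzed, with treatment differences and 95% confidence intervals for those analyzed. A between-product comparison can therefore be expected, although Section 12.4 names no model for these events. Meanwhile the trial collects pump alarms, which do not depend on suspicion or memory, and the plan makes no use of them here.

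**Working it through.** The plan gives no occlusion rate, margin or power, so there is no figure to reproduce. The check sets the sections side by side and then adds an illustration.

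**Recall interval.** The flow chart places contacts at day 1, day 7 and weeks 2, 4, 6 and 7 of each period. The longest nominal gap is 14 days. With the windows (week 4 contact up to 1 day early, week 6 visit up to 3 days late) it can reach 14 + 1 + 3 = 18 days.

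**What each record can show.**
- Patient report: that a set was changed and why the subject says so. The reason is given with knowledge of the product.
- Alarm record: that the pump raised an alarm, independent of the subject's view. It does not capture silent occlusions.
- Rewind and prime records: that a change took place and when, since Section 6.3.2.3 requires set and reservoir to be changed together. They do not show why.

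**Illustration of differential reporting.** Inputs from the plan: 49 days per period (7 weeks); "The Subjects should be instructed to routinely change infusion set in intervals not exceeding 3 days" (2 days for one set type); 36 subjects after dropout (Section 12.2).

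- Changes per subject and period at one per 3 days: 49 / 3 = 16.3.
- Changes per product, N: 36 × 49 / 3 = 588 (653 with all 40 subjects).

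Assumptions, not document values: the event rate r per set is the same for both products, and one product is reported f times as readily. Expected counts are a = N × r and b = f × a. On the log scale SE = √(1/a + 1/b), and the shift is d = ln(f) / SE. The chance of a nominally significant difference (two-sided 5%) is 1 − Φ(1.96 − d) + Φ(−1.96 − d).

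For r = 2% and f = 1.5: a = 11.8, b = 17.6, SE = 0.376, d = 0.405 / 0.376 = 1.08, and the chance is 19%.

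| r | a | f = 1.25 | f = 1.5 | f = 2 |
|---|---|---|---|---|
| 1% | 5.9 | 7% | 12% | 28% |
| 2% | 11.8 | 9% | 19% | 49% |
| 5% | 29.4 | 15% | 40% | 87% |

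The calculation treats the two counts as independent Poisson counts and ignores clustering within subjects. It is rough where counts are small. The expected ratio equals f by construction, so the table shows sensitivity and is not evidence that reporting will differ.

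**The case against.** The plan is not without safeguards. An event needs an actual set change, so only the trigger is subjective. Suspected sets are returned for viewing. Section 6.3.2.4 trains subjects to report set-change information. Unexplained hyperglycemia, one of the three triggers, is in the diary, has a threshold of 300 mg/dL in Section 9.1.7, and is checked against CareLink under Section 6.3.2.2. The endpoint is openly labelled as patient-reported and is one of many secondary items in an exploratory trial. These points stand and keep the matter modest. They do not remove it: the site that views the sets also knows the product, no reporting form is named, and nothing says that any of these checks changes the count.

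A reader might infer more than the documents support:

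- *That occlusion is a stated safety objective.* No objective in Section 4 names occlusion or pump compatibility; the nearest is the measurement of HCL parameters. The microscopically confirmed standard appears only in the background, for a cited study.
- *That forgetting alone biases the comparison.* In a crossover each subject is questioned on the same schedule under both products. Equal forgetting lowers both counts, and a biased ratio needs forgetting or reporting to differ by product.
- *That early changes found from rewinds and primes would be an objective replacement.* They record the same changes that the subject chose to make. They would also include changes prompted by the protocol: before meal tests (Section 6.3.4) and under supervision at Visits 2 and 14 (Section 6.3.2.3).
- *That a premature change has no reference at all.* Section 6.3.2.3 gives an upper limit for the routine interval. The lack of a numeric early cut-off is a minor gap.

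**Conclusion.** The concern holds in a limited form. As defined and collected, the occlusion count can differ between products through suspicion or reporting alone, and the plan does not use the alarm data that would help a reader judge this. The documents support neither a direction nor a size. It would be wrong to infer that the count will be raised on the newer insulin, or by any particular ratio, because such figures come entirely from assumed rates. The range of 12% to 40% for 1.5-fold differential reporting shows only that a moderate difference in reporting could matter at event rates of 1% to 5% of sets. The primary meal-test endpoint is unaffected. This is a worthwhile, low-cost improvement to one secondary endpoint.

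**What to change.** In Sections 4, 6.5.2 and 12.4:

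1. Keep the patient-reported count, but report it per product split by stated reason: occlusion, leakage, unexplained hyperglycemia.
2. Add a count, per product, of pump occlusion or no-delivery alarms taken from the CareLink uploads. Section 6.3.2 says only that alarms are uploaded, so this assumes that these alarm types can be identified in the files. That should be confirmed before the wording is fixed.
3. Use rewind and prime records only to confirm and date reported set changes, not as a separate endpoint.
4. State that the two counts are to be read together, since alarms miss silent occlusions and the patient report depends on suspicion.

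The cost is endpoint wording, recording the stated reason when subjects are already being questioned, and some extraction and programming time. No new subject procedure is needed, and nothing in clinical management changes.
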